6.4.3 Other Observations Related to Safety

6.4.3.1 Solicited Adverse Events

The following list of anticipated adverse events is solicited from subjects via the Subject Diary from the date of enrollment through the 7th day after receiving the last study treatment.

- gas (flatulence)
- abdominal distension or bloating
- rectal irritation or pain
- chills/severe shivering
- abdominal pain or cramping
- increased diarrhea
- constipation
- rectal bleeding
- nausea
- vomiting
- fever $\geq 38.0^{\circ}\text{C}$ (100.4°F)

Frequency and severity of the solicited AEs will be recorded in the Subject Diary.

6.4.3.2 Major Complications of Recurrent CDI

The frequencies of major complications of recurrent CDI including death, septic shock, toxic megacolon, colonic perforation, emergency colectomy, or ICU admission will be collected through the 24-month telephone assessment.

6.4.3.3 Pre-existing Conditions

A pre-existing condition is one that is present at the start of the study and is to be recorded at the time of the screening or baseline visits. Pre-existing conditions are assessed at the 3-, 6-, 12-, and 24-month telephone assessments. The assessment of pre-existing conditions includes discussion with the subject to determine if the condition improved, unchanged, worsened or resolved since completion of study treatment.

6.5 Efficacy Variables

The efficacy variables include the following:

- Treatment success, defined as the absence of CDI diarrhea without the need for retreatment with *C. difficile* anti-infective therapy or fecal transplant (FT) through 56 days after administration of the last study enema.
- SF-36 scores obtained at the 8-week assessments visits as compared to those obtained at the Screening visit.

7 STATISTICAL METHODS

7.1 General Methodology

All statistical tests will be performed using SAS® [REDACTED]. For continuous variables, descriptive statistics (number of subjects [N], mean, standard deviation [SD], median, inter-quartile range [IQR], minimum, and maximum) will be generated. For discrete/categorical variables, the number and percentage of non-missing subjects will be generated. Descriptive statistics will be provided for all subjects. [REDACTED]

[REDACTED] Subject listings of all data from the eCRFs as well as any derived variables will be presented.

[REDACTED]

[REDACTED]

[REDACTED]

[REDACTED]

[REDACTED]

[REDACTED]

7.8 Examination of Subgroups

Subgroup analysis of age (< 65 years, ≥ 65 years), sex (Female, Male), ethnicity (Hispanic or Latino, or Not Hispanic or Latino), race group (American Indian or Alaskan Native, Asian, Black or African American, Native Hawaiian or other Pacific Islander, White, and Other, as well as White and Non-white), and number of previous episodes of CDI recurrence at baseline will be conducted on the efficacy and safety analysis.

8 STATISTICAL ANALYSIS

8.1 Disposition of Subjects

A summary table will present subject disposition for all subjects. The table will show the number of RBX2660 treated subjects enrolled and the number of enrolled subjects not treated followed by the number of subjects in the study population as well as the number of historical controls included in the study. [REDACTED]

[REDACTED]

[REDACTED]

Discontinuation will be categorized by reason as a percentage of the number of all subjects in study population.

[REDACTED]

[REDACTED]

[REDACTED]

8.3 Baseline Assessments

Baseline assessments are collected within 30 days before study treatment administration. Summaries for age (years), sex, ethnicity, and race will be provided for the Full Analysis Set. Baseline BMI and employment status will also be summarized. *C. difficile* infection history will be summarized by total number of episodes and by each episode. The following will be summarized for each episode of CDI: duration (days), treatment administered, hospitalization with duration (if applicable) and available *C. difficile* test results.

For Form SF-36, the results obtained at the Screening visit will be used for the baseline assessment.

[REDACTED]

- [REDACTED]
- [REDACTED]
- [REDACTED]
- [REDACTED]
- [REDACTED]
- [REDACTED]

8.4 Demographic and Other Baseline Characteristics

All baseline summaries will be based on the Full Analysis Set and the Enrolled populations. Descriptive statistics (number of subjects [N], mean, standard deviation [SD], median, interquartile range [IQR], minimum, and maximum for continuous variables and number of

subjects [N] and the percentage for categorical variables) will be provided for all baseline measures.

8.5 Prior and Concomitant Therapy

The World Health Organization (WHO) Drug Dictionary [REDACTED] will be used to classify medications by preferred term and WHO Anatomical Therapeutic Chemical (ATC) level-4 classification of ingredients. Listings of all concomitant medications will be made by WHO ATC classification of ingredients and by preferred term.

8.6 Analysis of Safety

The Full Analysis Set will be used to summarize all adverse event data, unless otherwise specified. The method of analyzing adverse event is described [REDACTED]. Adverse events from the historical control subjects will be summarized and will be included in listings.

8.6.1 Adverse Events

A summary of adverse events, TEAEs, non-serious TEAEs, and serious TEAEs will be summarized using counts of the number of events and frequencies (counts and percentages) of the number of subjects in the Full Analysis Set. The frequency of each preferred term (PT) within the primary system organ class (SOC) as well as overall primary SOC frequency will be presented. A subject with multiple events coded to the same PT within a primary SOC will be counted only once for the PT within the primary SOC. Likewise, a subject with multiple events coded to the same SOC will be counted only once within the SOC. Adverse events and serious adverse events will also be summarized by onset timepoint by system organ class (SOC) and preferred term (PT): [REDACTED]

[REDACTED]

[REDACTED] Adverse events will be counted in the interval in [REDACTED]

which the start date of the event occurs. For subjects with multiple instances of the same event, the events will be counted once within each interval that the event starts.

An overall summary of AEs will present the frequency of all TEAEs, serious TEAEs, and TEAEs leading to death for the Full Analysis Set, as well as the frequency of the following for the RBX2660 treatment group:

- TEAEs related to RBX2660
- TEAEs related to enema procedure
- TEAEs related to *C. difficile* disease
- TEAEs related to a pre-existing condition
- Serious TEAEs related to RBX2660
- Serious TEAEs related to the enema procedure
- Serious TEAEs related to *C. difficile* disease
- Serious TEAEs related to a pre-existing condition.

Frequency of occurrence and number and percentage of subjects experiencing an event will be presented by SOC and PT using the Safety Population for the following:

- TEAEs by maximum severity
- TEAEs by relatedness to RBX2660
- TEAEs by relatedness to *C. difficile* disease
- TEAEs by relatedness to enema procedure
- TEAEs by relatedness to pre-existing condition
- Serious TEAEs
- Serious TEAEs by maximum severity
- Serious TEAEs by relatedness to RBX2660
- Serious TEAEs by relatedness to *C. difficile* disease
- Serious TEAEs by relatedness to enema procedure
- Serious TEAEs by relatedness to pre-existing condition

For the summary of AEs by maximum severity, if a subject has multiple events occurring in the same SOC or same PT, then the event with the highest severity will be counted. For AEs reported by causality, if a subject has multiple events occurring in the same SOC or same PT, the event with the highest association will be summarized.

A summary of TEAE and serious TEAE characteristics (severity, relatedness to RBX2660, relatedness to *C. difficile* disease, relatedness to enema procedure, and relatedness to pre-existing condition by outcome) will be presented for the Safety Population.

A summary of TEAE and serious TEAE characteristics (severity, relatedness to RBX2660, relatedness to *C. difficile* disease, relatedness to enema procedure, and relatedness to pre-existing condition by outcome) by SOC will also be presented for the Safety Population.

For data presentation, SOC will be ordered alphabetically, with PT sorted by decreasing total frequency. No inferential statistics will be provided for the AE data.

Subject listings will be presented for all AEs and for SAEs.

8.6.2 Other Analyses Related to Safety

8.6.2.1 Subject Diary including Solicited Adverse Events and Compliance

All solicited adverse events recorded in the Subject Diary will be summarized utilizing frequencies, proportions and 95% CIs for categorical variables and using the descriptive statistics as listed in Section 7.1 for continuous variables.

For each solicited event, severity scores will be summarized as both categorical and continuous values. For continuous summaries, severity scores will be identified as either pre-treatment or post-treatment, and the average for each period will be calculated across individual subjects.

Baseline for continuous summaries will be considered the average during the pre-treatment period. For categorical summaries, if a subject reports more than one severity score on the same date, the maximum severity will be used. Baseline for categorical summaries will be considered the last non-missing assessment prior to the first enema.

For each categorical summary of event frequency, a two-sided 95% CI will be calculated using the normal approximation of the binomial.

The following summaries will be produced relative to both the first and second enema:

- Frequency of severity scores on day of enema administration
- Frequency of severity scores on day 1 through day 7 post-treatment
- Frequency of maximum post-treatment severity score

The following summaries will be produced:

- Summary of average severity score and change from baseline
- Shift from baseline to 7-day post-treatment severity score
- Shift from baseline to maximum post-treatment severity score

Compliance in returning the Subject Diary will be calculated by dividing the number of diaries turned in, whether complete or not, by the number of diaries expected to be turned in.

Furthermore, compliance will be summarized by calculating the proportion of subjects who turned in “complete” diaries, where complete is defined as answering all 14 daily questions for at least 80% of the expected number of diaries.

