### 8.3 Analysis of Efficacy

The primary endpoint is: Efficacy, measured by the recurrence-free rate of CDI diarrhea without the need for retreatment with *C. difficile* anti-infective therapy or fecal transplant through 56 days after completion of study treatment with RBX2660. The primary analysis will compare the proportion of subjects in the treatment arm who are recurrence-free to the proportion of historical controls who are recurrence-free. [REDACTED]

[REDACTED] An efficacy and safety data-received-to-date analysis will be conducted on the treatment group subjects when approximately 100 of them

complete their 8-week assessment. [REDACTED]

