4 STUDY DESIGN

4.1 General Design

This is a prospective, multicenter, open-label study assessing the efficacy and safety of RBX2660 as an adjunct to antibiotics for the treatment of recurrent CDI. Up to approximately 150 subjects will be enrolled in this study and receive RBX2260. Approximately 100 historical controls will be chosen from a retrospective chart review of patients treated with antibiotics for recurrent CDI who match key inclusion/exclusion criteria from the study.

Subjects who meet all inclusion and exclusion criteria, including having a positive *C. difficile* test within 60 days prior to enrollment and experiencing either a) at least two recurrences after a primary episode (diagnosis must include at least one positive *C. difficile* test on record within 60 days prior to enrollment) and have completed at least two rounds of standard-of-care oral antibiotic therapy or b) have had at least two episodes of severe CDI resulting in hospitalization prior to enrollment, will receive open-label treatment with RBX2660. One study treatment consists of two RBX2660 enemas administered 7 ± 2 days apart; the second enema may be administered sooner if CDI diarrhea reoccurs in less than 7 days. Subjects will already be taking or will start a course of antibiotics to control recurrent CDI diarrhea at the time of enrollment, [REDACTED]

[REDACTED] An in-office follow-up visit will occur at 8 weeks after completing study treatment for the assessment of AEs, efficacy, collection of the Subject Diary, and blood tests. Telephone assessments for AEs including serious adverse events (SAEs) and the new onset of chronic diseases and CDI symptoms will occur at weeks 1, 2, 3, and 4 and at 3, 6, and 12 months after completing study treatment. Assessment of serious adverse events and the new onset of chronic diseases will occur via phone call at 24 months after completing study treatment. Subjects will keep a detailed Subject Diary to assess for solicited adverse events from the date of enrollment to one week after completing study treatment (second enema). Treatment

failures (as determined by the site investigator at the time of CDI recurrence) are eligible to receive another therapy deemed most appropriate by their study investigator.

[REDACTED]

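### The normal-approximation 95% CI for diary-solicited adverse events gives [0%, 0%] at zero events and upper limits that are too low at small counts

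*SAP*

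**What the plan says.** SAP section 8.6.2.1 sets the general requirement: "All solicited adverse events recorded in the Subject Diary will be summarized utilizing frequencies, proportions and 95% CIs for categorical variables". For each categorical summary of event frequency it then fixes the method: "a two-sided 95% CI will be calculated using the normal approximation of the binomial". The rule carries no condition on the number of events.

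The same section lists three summaries, each produced relative to the first and the second enema. One tabulates severity scores on the enema day itself. The next covers the week that follows: "Frequency of severity scores on day 1 through day 7 post-treatment". The third takes each subject's worst score after treatment.

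SAP section 6.4.3.1 lists 11 solicited events. SAP section 3.4 makes their frequency and severity the first secondary endpoint. On the denominator, SAP section 4.1 states: "Up to approximately 150 subjects will be enrolled in this study". Protocol section 8.4 asks for 95% CIs on solicited events but names no method. Neither document gives an expected rate for any diary event.

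**The concern.** The normal approximation estimates the standard error from the observed proportion. When the observed proportion is near zero, so is the standard error, and at zero events the interval has no width. The table would then state that an event not seen in a limited sample has a rate of exactly 0%. At one to three events the lower limit is negative and the upper limit is too close to zero.

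The error is one-sided. For a rare diary event the printed upper limit sits below rates that the data still allow. A reader of a safety table uses that limit to judge how frequent an event could be, so this is the limit that most needs to be right.

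**Working it through.** **Inputs.** Two-sided 95% level and normal approximation: SAP 8.6.2.1. Denominator n = 150: upper bound from SAP 4.1. A second value, n = 100, comes from Protocol 8.3, which describes a "data-received-to-date analysis will be conducted on the treatment group subjects when approximately 100 of them" complete the 8-week assessment. Event rates are not in the documents, so a range is used. The plan states no interval of its own to reproduce.

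**Formulas**, with x events, p = x/n and z = 1.96:

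- Normal approximation (Wald): p ± z·√(p(1 − p)/n)
- Exact (Clopper-Pearson): lower limit = 2.5% quantile of Beta(x, n − x + 1); upper limit = 97.5% quantile of Beta(x + 1, n − x)
- Coverage at true rate π: the sum of the Binomial(n, π) probabilities over all x whose interval contains π

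**Limits at n = 150.** For x = 0, p = 0 and the Wald half-width is 1.96·√(0/150) = 0. The exact upper limit is 1 − 0.025^(1/150) = 2.43%. For x = 1, p = 0.67% and the half-width is 1.96·√(0.00667 × 0.99333/150) = 1.30 points.

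| Events | Wald | Exact | Wald upper limit too low by |
|---|---|---|---|
| 0 | 0.00% to 0.00% | 0.00% to 2.43% | 2.43 points |
| 1 | −0.64% to 1.97% | 0.02% to 3.66% | 1.69 |
| 2 | −0.50% to 3.17% | 0.16% to 4.73% | 1.56 |
| 3 | −0.24% to 4.24% | 0.41% to 5.73% | 1.49 |
| 5 | 0.46% to 6.21% | 1.09% to 7.61% | 1.40 |
| 30 | 13.60% to 26.40% | 13.92% to 27.30% | 0.90 |

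**Coverage at n = 150.**

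| True rate | Wald | Exact | Wilson | Wald upper limit below truth (nominal 2.5%) | Wald lower limit above truth |
|---|---|---|---|---|---|
| 0.5% | 52.8% | 99.3% | 96.0% | 47.1% | 0.0% |
| 1% | 77.8% | 98.2% | 93.5% | 22.1% | 0.1% |
| 2% | 80.0% | 98.9% | 96.8% | 19.6% | 0.3% |
| 3% | 93.6% | 97.4% | 95.2% | 5.8% | 0.6% |
| 5% | 93.7% | 96.3% | 94.3% | 5.5% | 0.8% |
| 10% | 92.6% | 97.2% | 96.0% | 6.0% | 1.4% |

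The 1% row can be checked by hand. The only count whose upper limit lies below 1% is zero, and its probability is 0.99^150 = 22.1%. At 2%, the one-event upper limit of 1.97% also misses, so zero and one event both count.

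Wald coverage is 94.4% at 20% and 95.0% at 30%. On a grid in steps of 0.05 points from 0.1% to 30%, it last falls below 85% at a rate of 2.2%. It still dips to 85.8% between 3% and 5%. Exact coverage on that grid is never below 95.0%.

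**Coverage at n = 100.** Wald coverage is 39.4%, 63.3%, 86.6%, 80.2%, 90.6% and 87.7% at 0.5%, 1%, 2%, 3%, 4% and 5%.

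**How often small counts would arise.** At n = 150 the chance of 0 to 3 events in a cell is 93.5% at an assumed rate of 1%, 64.7% at 2%, 33.8% at 3% and 5.5% at 5%. The listed tables amount to 11 events × 2 enemas × 3 summaries = 66. If days 1 to 7 are shown singly, there are 9 summaries per enema and 11 × 2 × 9 = 198. Each is then split by severity score.

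**The case against.** **Only descriptive.** SAP 8.6.1 rules out inferential statistics for adverse event data, and no visible decision depends on these intervals. Counts and listings would still show the reader that 0 of 150 had the event. This stands and limits the importance of the point. It does not justify printing a limit under a 95% label that it does not meet.

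**Sparse cells are assumed.** This also stands. The serious loss of coverage needs cell rates of about 2% or less at n = 150, and nothing in the documents shows that high scores are rare. The text also leaves open whether the interval belongs to each severity score or only to any occurrence of the event; on the second reading fewer cells are affected. The figures of 66 and 198 count tables, not sparse cells. They use the 11-event list, whereas Protocol 8.4 lists 17 events, which would make the counts larger. Some zero cells could be structural: if diary scores follow Protocol Table 7-1, grades marked NA can never occur and need no interval.

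**The n = 100 figures are conditional.** They apply only if diary intervals are produced at that analysis. Diary collection ends 7 days after the second enema (Protocol 6.3), so more than 100 subjects could have diary data by then.

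**The wording might mean something else.** A continuity-corrected interval would not be exactly [0%, 0%] at zero events, but its upper limit would be only 0.33% at n = 150. Its coverage is adequate at 2% (95.1%) but unchanged at 0.5% and 1% (52.8% and 77.8%). The Wilson interval also derives from a normal approximation, but the SAP wording would not ordinarily be read that way. If Wilson is meant, the SAP should say so. Parts of SAP section 7 are redacted and could hold a general rule; section 8.6.2.1 is nevertheless explicit for these tables.

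**Conclusion.** The concern holds. As written, the rule gives a zero-width interval at zero events, negative lower limits at one to three events of 150, and upper limits about 1.4 to 2.4 points too low at zero to five events. At n = 150 coverage is 52.8% to 80.0% for true rates from 0.5% to 2%, with the misses almost entirely on the side that understates risk.

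This rests on the Wald reading of the SAP wording and on some cells having rates of about 2% or less. The arithmetic is certain; how many cells are affected is not known from the documents. The reach is limited to the diary intervals for the first secondary endpoint. The primary endpoint, the AE and SAE tables in SAP 8.6.1 and the major complications in SAP 8.6.2.2 are untouched. It should be corrected, but it does not threaten the trial's main conclusion.

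**What to change.** In SAP section 8.6.2.1, replace the normal approximation with the exact (Clopper-Pearson) method for all solicited-event proportions. The Wilson score method is an acceptable alternative: it is closer to nominal on average but can fall somewhat short at very low rates (91.0% at a 0.5% rate with n = 100). State in the same sentence whether the interval is given for each severity score or for any occurrence, and omit it for grades that cannot occur. Protocol section 8.4 names no interval method and needs no change on this point.

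The cost is one phrase in the SAP and a software option. Exact intervals are slightly wider for common events: at n = 150, 10.25 instead of 9.60 percentage points at 15 events, and 13.38 instead of 12.80 at 30 events.

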8.6.2.2 Major Complications of Recurrent CDI

Major complications of recurrent CDI include death, septic shock, toxic megacolon, colonic perforation, emergency colectomy, or ICU admission collected through the 24-month telephone assessment. Incidence of major complications of recurrent CDI will be summarized in a table.

A listing of all major complications recurrent CDI throughout the study will be generated.

[REDACTED]

[REDACTED]

[REDACTED]

[REDACTED]

[REDACTED]

[REDACTED]

[REDACTED]

[REDACTED]

8.7 Analysis of Efficacy

8.7.1 Treatment Success

Treatment success is the primary efficacy endpoint and the analyses will be performed on the Evaluable Population. The primary endpoint will be summarized by frequencies and percentages

[REDACTED]

[REDACTED] The analysis of efficacy will be repeated using the Full Analysis Set and Per Protocol populations. Sensitivity analyses will also be conducted using the Full Analysis Set where missing responses are imputed using a best-case scenario where missing responses are treated as successes.

[REDACTED]

[REDACTED]

[REDACTED]

[REDACTED]

[REDACTED]

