### **8.5 Management of Missing Data**

The safety assessment will be analyzed using all available data only. No imputation of missing data is planned for the safety assessment. Efficacy assessments will also be analyzed using all available data. [REDACTED]

[REDACTED]  
[REDACTED]  
[REDACTED]  
[REDACTED]

[REDACTED]  
[REDACTED]  
[REDACTED]  
[REDACTED]  
[REDACTED]

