4.5 Determination of Sample Size

Approximately up to 150 subjects will be enrolled in this study and receive RBX2660; and another 100 historical controls with recurrent CDI diarrhea will also be included in the study based on a retrospective chart review.

The primary analysis will compare the proportion of subjects in the treatment arm who are recurrence-free to the proportion of historical controls who are recurrence-free. [REDACTED]

[REDACTED]
[REDACTED]
[REDACTED]
[REDACTED]

[REDACTED]

[REDACTED]

[REDACTED]

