6.3 Analysis Populations

Enrolled Population: includes all subjects enrolled into the study, including subjects in the historical control arm.

Safety Population: includes all subjects enrolled into the study who received any study treatment with RBX2660; this does not include subjects in the historical control arm.

Full Analysis Set (FAS) Population: includes the Safety Population and subjects in the historical control arm.

Evaluable Population: includes the FAS subjects who were evaluable for treatment outcome (e.g., exclude subjects that discontinued from the study prior to determination of treatment failure and were not followed for at least 56 days (day 49 – 63) after the last treatment date).

Per Protocol Population: includes subjects from the Evaluable Population, excluding:

- Subjects from the Safety Population that did not complete 2 enemas

- Subjects that received fecal microbiota transplant before the 8-week follow-up and lacked a documented recurrence of CDI (Treatment Failure eCRF)
- Violations to the inclusion or exclusion criteria, including protocol definition of recurrent CDI two hospitalizations for CDI or 3 recurrent CDI events
- Received prohibited medication during the 8-week follow-up period

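### The one visible missing-data sensitivity analysis imputes success in both arms, so it does not test the least favourable case for the treatment difference if both arms have missing outcomes

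*SAP*

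**What the plan says.** SAP 4.5 sets the primary contrast: to "compare the proportion of subjects in the treatment arm who are recurrence-free to the proportion of historical controls who are recurrence-free". For treatment success, SAP 8.7.1 says "the analyses will be performed on the Evaluable Population".

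SAP 6.3 defines that population so that it "includes the FAS subjects who were evaluable for treatment outcome", with the example that it would "exclude subjects that discontinued from the study prior to determination of treatment failure" if they were also not followed to about day 56 (day 49 to 63). The Full Analysis Set "includes the Safety Population and subjects in the historical control arm".

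SAP 8.7.1 then adds two things that can be read. First, "The analysis of efficacy will be repeated using the Full Analysis Set and Per Protocol populations"; the rule for subjects without an outcome in that repeat is not visible. Second, there is a sensitivity analysis on the "Full Analysis Set where missing responses are imputed using a best-case scenario where missing responses are treated as successes". No distinction between the arms is visible.

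Protocol 8.5 says "Efficacy assessments will also be analyzed using all available data", and the lines after it are redacted. Text before and after the visible sentences of SAP 8.7.1 is redacted too. No missing-data rate is visible for either arm.

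**The concern.** The comparison is open-label and non-randomised, so whether the advantage over controls survives missing outcomes is a main question for the reader. The two arms lose information in different ways. Treated subjects are telephoned in weeks 1 to 4 and seen at 8 weeks. Controls come from a chart review in which patients are not contacted (Protocol Appendix 1, A4), so an outcome absent from the chart cannot be recovered by asking.

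The Evaluable rule adds an asymmetry. A recurrence makes a subject evaluable whenever it occurs, but a success needs about 56 days of follow-up. A control with a short chart record and no recorded recurrence is dropped, while an early failure stays. That can lower the observed control rate and enlarge the difference. Missing controls who were in fact recurrence-free are therefore a realistic scenario.

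A rule that gives every missing subject the same value moves both proportions the same way, so much of its effect cancels in the difference. What could be missed is the combination that hurts RBX2660 most: missing treated subjects who failed and missing controls who succeeded.

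**Working it through.** The plan shows no figure to reproduce: the sample-size assumptions and the details of the primary test are redacted. The check is therefore algebra, followed by an illustration.

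**Algebra.** In each arm let s be observed successes, m missing outcomes, n the Full Analysis Set size and f = m/n (T = treated, C = control). Let pT and pC be the unknown success rates among the missing. Then

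D(pT, pC) = (sT + pT·mT)/nT − (sC + pC·mC)/nC.

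- Missing = success in both arms is D(1, 1).
- Missing = failure in both arms is D(0, 0).
- The lowest possible value is D(0, 1) and the highest is D(1, 0).

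Subtracting:

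- D(1, 1) − D(0, 0) = fT − fC
- D(1, 1) − lowest = fT, and highest − D(1, 1) = fC
- D(0, 0) − lowest = fC, and highest − D(0, 0) = fT
- highest − lowest = fT + fC

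If fT and fC are both above zero, neither same-direction rule reaches either bound. If fT = fC, the two rules give the same answer, and running both would suggest a robustness that was not tested. If fC = 0, missing = success is the upper bound and missing = failure the lower. If fT = 0, these are reversed.

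**Inputs for the illustration.**

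- 150 treated and 100 controls: SAP 4.5.
- Control success 35%: assumed from the 65% recurrence after two relapses in Protocol Appendix 1, A3 (100 − 65). 40% is a second assumed value.
- RBX2660 success 70% or 80%, and missing fractions of 0 to 20%: assumed, because the documents show none.
- Intervals: 95% Wald, my choice.

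**Case A: 80% v 40% observed, 10% v 20% missing.** Treated: 15 missing, 108 successes among 135. Controls: 20 missing, 32 successes among 80.

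- Evaluable: 108/135 − 32/80 = 0.80 − 0.40 = 0.40
- Missing = success in both: 123/150 − 52/100 = 0.82 − 0.52 = 0.30
- Missing = failure in both: 108/150 − 32/100 = 0.72 − 0.32 = 0.40
- Lower bound: 0.72 − 0.52 = 0.20
- Upper bound: 0.82 − 0.32 = 0.50

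Interval for the lower bound: SE = √(0.72·0.28/150 + 0.52·0.48/100) = √0.00384 = 0.062, so 0.20 ± 0.12, about 8 to 32 points.

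**Case B: 70% v 35% observed, 20% missing in each arm.** Treated: 30 missing, 84 successes among 120. Controls: 20 missing, 28 successes among 80.

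- Missing = success in both: 114/150 − 48/100 = 0.76 − 0.48 = 0.28, interval 0.161 to 0.399
- Missing = failure in both: 84/150 − 28/100 = 0.56 − 0.28 = 0.28
- Lower bound: 0.56 − 0.48 = 0.08; SE = √(0.56·0.44/150 + 0.48·0.52/100) = 0.064, interval −0.046 to 0.206
- Upper bound: 0.76 − 0.28 = 0.48

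**Other missing fractions, at about 70% v 35% observed (whole subjects):**

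| Missing T / C | Success in both | Failure in both | Lower | Upper |
|---|---|---|---|---|
| 10% / 10% | 0.317 | 0.317 | 0.217 | 0.417 |
| 10% / 20% | 0.247 | 0.347 | 0.147 | 0.447 |
| 10% / 0% | 0.377 | 0.277 | 0.277 | 0.377 |
| 0% / 10% | 0.290 | 0.390 | 0.290 | 0.390 |

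The first two rows show both rules inside the range. The last two show that with missing outcomes in one arm only, they are the bounds.

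**The case against.** The strongest objection is the redaction. Text is blacked out on both sides of the sentence in SAP 8.7.1, in much of SAP section 7, and in Protocol 8.5 directly after the sentence on available data. The wording of 8.7.1 (a plural, an also, a best-case label) fits a companion analysis in hidden text. The Full Analysis Set repeat also needs some rule for subjects without an outcome, and that rule may be less favourable. This stands: a reader might infer that no worst-case analysis is planned, and the documents do not support that.

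Second, controls may have no missing outcomes. Charts are selected, and Appendix 1, A4 requires a log of excluded records, so charts without an outcome may never enter the control set. Then same-direction imputation does bound the difference. This also stands. The Evaluable definition allows missing control outcomes but does not establish them, so the point is conditional.

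Third, a reader might infer that the stated rule flatters RBX2660. It gives the highest possible RBX2660 rate, but the endpoint is a difference. In Case A the rule shrinks the difference from 40 to 30 points, and even the worst case of 20 points has an interval above zero. So the rule is not biased in a known direction.

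Fourth, the rates and missing fractions are assumed. That is true of the sizes; the algebra does not depend on them.

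**Conclusion.** The point holds in a conditional form. The only visible missing-data sensitivity analysis imputes success across a set that includes the controls. If both arms have missing outcomes, neither it nor its mirror reaches the lower bound of the treatment difference. The stated rule sits above that bound by the treated missing fraction, and the mirror by the control missing fraction.

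Whether this changes the conclusion depends on unknown quantities. Under the assumptions of Case A the advantage survives the worst case (20 points, about 8 to 32). Under those of Case B it does not clearly survive (8 points, about −5 to 21), although the stated rule gives 28 points (16 to 40).

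It does not follow that same-direction imputation can never bound the difference, since with one arm complete it does. Nor does it follow that the full plan lacks a stress test, because the neighbouring text cannot be read. The change is worth making because the case left untested by the visible text is a realistic one and the remedy is small.

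**What to change.** In SAP 8.7.1, specify a Full Analysis Set sensitivity analysis with missing RBX2660 outcomes counted as failures and missing control outcomes as successes. Keep the opposite assignment (RBX2660 success, control failure) as the upper bound. Add a tipping-point grid over the two missing-outcome success rates, pT and pC, showing where the conclusion changes. The stated rule then appears as one corner of that grid. Report the number of missing outcomes by arm beside it.

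First check the redacted text of SAP 8.7.1, SAP section 7 and Protocol 8.5: if an arm-specific analysis is already there, no change is needed.

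The cost is a few lines of SAP text and one extra table, and the worst-case figure will look less favourable than the ones now visible.
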